9.1 Definition of pollen seasons

Each site was allocated to a pollen region prior to unblinding.

The different pollen seasons varied across the selected pollen regions both in intensity and duration.

BPS

For each pollen region and year the BPS were defined as follows:

Start date: The start date of the BPS is defined as the first day of 3 consecutive days with pollen count larger than or equal to 30 grains/m³

Stop date: The stop date of the BPS is defined as the last day in the last occurrence of 3 consecutive days with pollen count larger than or equal to 30 grains/m³

Alder, Hazel and Oak

The alder, hazel, oak pollen seasons were defined as the days included in any of the alder, hazel, and oak pollen seasons:

Start date: The start date of the pollen season is defined as the first day of 3 consecutive days with pollen count larger than or equal to 10 grains/m³

Stop date: The stop date of the pollen season is defined as the last day in the last occurrence of 3 consecutive days with pollen count larger than or equal to 10 grains/m³

Based on experience from trial TT-04, it is anticipated that there will be a high degree of overlap between the alder and hazel seasons. As such, a combined alder-hazel season is defined for each pollen station as follows:

[figure not shown]
Start date: The start date of the alder-hazel pollen season is the earliest of the alder season start date and hazel season start date

Stop date: The stop date of the alder-hazel pollen season is the latest of the alder season stop date and the hazel season stop date

TPS

The TPS is defined as all days included in any of the alder, birch, hazel, oak pollen seasons. The TPS is not necessarily a continuous period, an example is illustrated in Figure 3.

Figure 3: Example of tree pollen season with non-continuous period

In case of missing pollen counts for specific pollen stations one of the 3 approaches was applied prior to unblinding:

- For pollen stations with missing data between observed start and stop date of the season LOCF was applied.
- For pollen stations with either very sparse data or completely missing data, each station was assigned a neighboring station as close as possible to the original station where data was available. Pollen counts from the backup station was used and in addition a sanity check was made by looking into the historical pollen data for the original pollen station.

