Appendix D Final pollen season

pollen_station	Season	Cohort	Start_date	End_date	Average grains/m3	Neighbouring	comments
ATWIEN	ALDER	1	05-02-2022	30-03-2022	95,6		
CZTRIN	ALDER	1	13-02-2022	30-03-2022	110,1		
DEAACH	ALDER	1	09-02-2022	08-03-2022	47		
DEBOCH	ALDER	1	07-02-2022	13-03-2022	54,7		
DEBORS	ALDER	1	27-01-2022	25-03-2022	109,8		
DEDRES	ALDER	1	12-02-2022	24-03-2022	55		
DELEVE	ALDER	1	07-02-2022	13-03-2022	27,2		
DELOEW	ALDER	1	04-02-2022	22-03-2022	52,8		
DEMARB	ALDER	1	08-02-2022	23-03-2022	64,7		
DEMOEN	ALDER	1	07-02-2022	13-03-2022	34,7		
DKCOPE	ALDER	1	12-02-2022	15-03-2022	20		
FRSTRA	ALDER	1	02-02-2022	28-03-2022	324,8		
HUGYOE	ALDER	1	03-02-2022	26-03-2022	84,7		
HUMISK	ALDER	1	05-02-2022	01-05-2022	36,3		
HUPEST	ALDER	1	04-02-2022	30-03-2022	118,2		
HUSALG	ALDER	1	05-02-2022	03-04-2022	107,4		
HUSZE2	ALDER	1	15-02-2022	29-03-2022	65,2		
LTSIAU	ALDER	1	24-02-2022	28-03-2022	82,3		
LTVILN	ALDER	1	25-02-2022	05-04-2022	63,5		
PLBYDG	ALDER	1	13-02-2022	06-04-2022	171,7		
PLCRAC	ALDER	1	13-02-2022	28-03-2022	156,3		
PLKATO	ALDER	1	08-02-2022	04-04-2022	126,5		
PLLODZ	ALDER	1	13-02-2022	02-04-2022	180,8		
PLLUBL	ALDER	1	15-02-2022	29-03-2022	120,6		
PLPTRY	ALDER	1	08-02-2022	05-04-2022	175,1		
PLSZCZ	ALDER	1	05-02-2022	14-03-2022	51,5		
RUMOSC	ALDER	1	14-03-2022	12-04-2022			
SKBRAT	ALDER	1	09-02-2022	09-04-2022	113,6		
ATWIEN	ALDER	2	20-02-2023	11-03-2023	19,3		
BEBRUS	ALDER	2	08-02-2023	23-03-2023	133,4	NLLEID	completely missing
BEMARC	ALDER	2	07-02-2023	24-03-2023	153,8	DEMOEN	completely missing
CZTRIN	ALDER	2	07-03-2023	10-03-2023	27,5		
DEBOCH	ALDER	2	13-02-2023	22-03-2023	141,2		
DEDRES	ALDER	2	16-02-2023	03-03-2023	71,8		
DELEVE	ALDER	2	07-02-2023	24-03-2023	153,8	DEMOEN	partially missing
DELIPP	ALDER	2	16-02-2023	21-03-2023	83,1		

DELOEW	ALDER	2	15-02-2023	06-03-2023	76,5		
DEMARB	ALDER	2	22-02-2023	18-03-2023	63,4		
DEMOEN	ALDER	2	07-02-2023	24-03-2023	153,8		
DEMUNC	ALDER	2	16-02-2023	10-03-2023	38		
DKCOPE	ALDER	2	11-02-2023	03-04-2023	41,8		
DKVIBO	ALDER	2	01-03-2023	03-04-2023	12,8		
FRSTRA	ALDER	2	02-02-2023	14-03-2023	127,7		
HUGYOE	ALDER	2	17-02-2023	10-03-2023	45,3		
HUMISK	ALDER	2	21-02-2023	05-03-2023	18,9		
HUPEST	ALDER	2	17-02-2023	10-03-2023	25,3		
HUSALG	ALDER	2	18-02-2023	17-03-2023	25,3		
HUSZE2	ALDER	2	17-02-2023	02-03-2023	35,6		
LTSIAU	ALDER	2	19-03-2023	11-04-2023	46		
LTVILN	ALDER	2	14-03-2023	25-03-2023	138,5		
MONTREAL	ALDER	2	09-04-2023	11-05-2023	35,8		
NLLEID	ALDER	2	08-02-2023	23-03-2023	133,4		

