PLBIAL	ALDER	2	10-03-2023	24-03-2023	93,5		
PLBYDG	ALDER	2	17-02-2023	16-04-2023	24,3		
PLCRAC	ALDER	2	26-02-2023	14-03-2023	33,5		
PLKATO	ALDER	2	10-03-2023	14-03-2023	44,8		
PLLODZ	ALDER	2	03-03-2023	20-03-2023	54		
PLLUBL	ALDER	2	18-02-2023	31-03-2023	18,9	PLPTRY	completely missing
PLPTRY	ALDER	2	18-02-2023	31-03-2023	18,9		
PLSZCZ	ALDER	2	17-02-2023	16-04-2023	24,3	PLBYDG	completely missing
PLWROC	ALDER	2	01-03-2023	14-03-2023	46,5		
QUEBEC	ALDER	2	13-04-2023	09-05-2023	20,4		
SKBRAT	ALDER	2	17-02-2023	11-03-2023	43,2		
SKNITR	ALDER	2	17-02-2023	11-03-2023	43,2	SKBRAT	completely missing
ATWIEN	BIRCH	1	28-03-2022	03-05-2022	367,9		LOCF
CZTRIN	BIRCH	1	14-04-2022	15-05-2022	378,4		
DEAACH	BIRCH	1	23-03-2022	26-04-2022	260,5	DEMOEN	completely missing
DEBOCH	BIRCH	1	23-03-2022	29-04-2022	323,5		
DEBORS	BIRCH	1	16-04-2022	11-05-2022	324,8		
DEDRES	BIRCH	1	06-04-2022	11-05-2022	463,6		
DELEVE	BIRCH	1	22-03-2022	24-04-2022	221,4		
DELOEW	BIRCH	1	28-03-2022	09-05-2022	132,1		
DEMARB	BIRCH	1	09-04-2022	11-05-2022	556,8		
DEMOEN	BIRCH	1	23-03-2022	26-04-2022	260,5		
DKCOPE	BIRCH	1	27-04-2022	30-04-2022	41		

FRSTRA	BIRCH	1	24-03-2022	04-05-2022	228,2		
HUGYOE	BIRCH	1	28-03-2022	03-05-2022	185,2		
HUMISK	BIRCH	1	05-04-2022	14-05-2022	250,1		
HUPEST	BIRCH	1	26-03-2022	10-05-2022	175,5		
HUSALG	BIRCH	1	07-04-2022	12-05-2022	257,3		
HUSZE2	BIRCH	1	29-03-2022	14-05-2022	131,4		
LTSIAU	BIRCH	1	21-04-2022	24-05-2022	560,2		
LTVILN	BIRCH	1	26-04-2022	24-05-2022	389,2		
MONTREAL	BIRCH	1	08-05-2022	13-05-2022	150,9		
PLBYDG	BIRCH	1	13-04-2022	15-05-2022	1053,9		
PLCRAC	BIRCH	1	12-04-2022	13-05-2022	601		
PLKATO	BIRCH	1	08-04-2022	23-05-2022	1049,2		
PLLODZ	BIRCH	1	13-04-2022	14-05-2022	972,1		
PLLUBL	BIRCH	1	14-04-2022	13-05-2022	632,8		
PLPTRY	BIRCH	1	13-04-2022	14-05-2022	1002,3		
PLSZCZ	BIRCH	1	18-04-2022	03-05-2022	78,3		
QUEBEC	BIRCH	1	09-05-2022	14-05-2022	198,7		
RUMOSC	BIRCH	1	21-04-2022	13-05-2022			
SKBRAT	BIRCH	1	27-03-2022	12-05-2022	441,6		
ATWIEN	BIRCH	2	24-03-2023	24-04-2023	64,3		
BEBRUS	BIRCH	2	12-04-2023	01-05-2023	143,2	NLLEID	completely missing
BEMARC	BIRCH	2	02-04-2023	05-05-2023	329,1	DEMOEN	completely missing
CZTRIN	BIRCH	2	13-04-2023	06-05-2023	189,6		
DEBOCH	BIRCH	2	10-04-2023	05-05-2023	615,5		
DEDRES	BIRCH	2	17-04-2023	01-05-2023	68,2	DEMARB	partially missing
DELEVE	BIRCH	2	05-04-2023	14-04-2023	172,1		LOCF
DELIPP	BIRCH	2	17-04-2023	02-05-2023	212,9		
DELOEW	BIRCH	2	17-04-2023	05-05-2023	81,4		
DEMARB	BIRCH	2	17-04-2023	01-05-2023	68,2		

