DEMOEN	BIRCH	2	02-04-2023	05-05-2023	329,1		
DEMUNC	BIRCH	2	21-04-2023	05-05-2023	158,5		
DKCOPE	BIRCH	2	19-04-2023	05-05-2023	248,4		
DKVIBO	BIRCH	2	20-04-2023	14-05-2023	250,4		
FRSTRA	BIRCH	2	22-03-2023	05-05-2023	80,4		
HUGYOE	BIRCH	2	23-03-2023	24-04-2023	80,8		
HUMISK	BIRCH	2	16-04-2023	26-04-2023	338,8		LOCF
HUPEST	BIRCH	2	24-03-2023	26-04-2023	151,4		
HUSALG	BIRCH	2	12-04-2023	24-04-2023	613,4		
HUSZE2	BIRCH	2	24-03-2023	24-04-2023	141,3		

LTSIAU	BIRCH	2	19-04-2023	17-05-2023	162,7		
LTVILN	BIRCH	2	18-04-2023	15-05-2023	880,5		
MONTREAL	BIRCH	2	28-04-2023	24-05-2023	195,5		
NLLEID	BIRCH	2	12-04-2023	01-05-2023	143,2		
PLBIAL	BIRCH	2	17-04-2023	07-05-2023	277,5		
PLBYDG	BIRCH	2	17-04-2023	06-05-2023	283,7		
PLCRAC	BIRCH	2	13-04-2023	04-05-2023	260,2		
PLLODZ	BIRCH	2	16-04-2023	06-05-2023	464,1		
PLLUBL	BIRCH	2	16-04-2023	07-05-2023	327,4	PLPTRY	completely missing
PLPTRY	BIRCH	2	16-04-2023	07-05-2023	327,4		
PLSZCZ	BIRCH	2	17-04-2023	06-05-2023	283,7	PLBYDG	completely missing
PLWROC	BIRCH	2	15-04-2023	02-05-2023	409,7		
QUEBEC	BIRCH	2	05-05-2023	29-05-2023	243		LOCF
SKBRAT	BIRCH	2	25-03-2023	24-04-2023	138		
SKNITR	BIRCH	2	25-03-2023	24-04-2023	138	SKBRAT	completely missing

ATWIEN	HAZEL	1	30-01-2022	17-03-2022	30		
CZTRIN	HAZEL	1	10-02-2022	23-03-2022	100,4		
DEAACAH	HAZEL	1	09-02-2022	21-02-2022	81,1		
DEBOCH	HAZEL	1	28-01-2022	15-02-2022	55,3		
DEBORS	HAZEL	1	27-01-2022	24-02-2022	25,1		
DEDRES	HAZEL	1	28-01-2022	19-02-2022	31,9		
DELEVE	HAZEL	1	12-02-2022	18-02-2022	26,3		
DELOEW	HAZEL	1	28-01-2022	14-03-2022	23,2		
DEMARB	HAZEL	1	27-01-2022	13-03-2022	20,4		
DEMOEN	HAZEL	1	31-12-2021	15-02-2022	14,4		
FRSTRA	HAZEL	1	02-01-2022	13-03-2022	71,4		
HUGYOE	HAZEL	1	02-02-2022	24-03-2022	21,8		
HUMISK	HAZEL	1	05-02-2022	28-03-2022	53,9		
HUPEST	HAZEL	1	29-01-2022	31-03-2022	41,8		
HUSALG	HAZEL	1	05-02-2022	03-04-2022	69,3		

HUSZE2	HAZEL	1	03-02-2022	31-03-2022	47,1		
LTSIAU	HAZEL	1	12-03-2022	28-03-2022	64,2		
LTVILN	HAZEL	1	15-03-2022	26-03-2022	65,7		
PLBYDG	HAZEL	1	07-02-2022	24-03-2022	20,7		
PLCRAC	HAZEL	1	09-02-2022	21-03-2022	49		
PLKATO	HAZEL	1	09-02-2022	21-03-2022	46,2		
PLLODZ	HAZEL	1	12-02-2022	22-03-2022	22,3		LOCF
PLLUBL	HAZEL	1	13-02-2022	24-03-2022	42,1		
PLPTRY	HAZEL	1	09-02-2022	24-03-2022	31,4		
PLSZCZ	HAZEL	1	28-01-2022	30-01-2022	20,7		
RUMOSC	HAZEL	1	18-03-2022	12-04-2022			
SKBRAT	HAZEL	1	02-02-2022	01-05-2022	21,5		
ATWIEN	HAZEL	2	16-02-2023	10-03-2023	19,4		
BEBRUS	HAZEL	2	06-01-2023	18-02-2023	6	NLLEID	completely missing

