PLSZCZ	OAK	1	07-05-2022	13-05-2022	24,3		
QUEBEC	OAK	1	18-05-2022	26-05-2022	94,2		
RUMOSC	OAK	1	07-05-2022	22-05-2022			
SKBRAT	OAK	1	25-03-2022	22-05-2022	115,4		
ATWIEN	OAK	2	21-04-2023	11-05-2023	39,5		
BEBRUS	OAK	2	03-05-2023	21-05-2023	46,1	NLLEID	completely missing
BEMARC	OAK	2	10-04-2023	21-05-2023	63,5	DEMOEN	completely missing
CZTRIN	OAK	2	11-05-2023	14-05-2023	29,8		
DEBOCH	OAK	2	09-04-2023	16-05-2023	89,2		

DEDRES	OAK	2	17-05-2023	25-05-2023	30,7	DEMARB	partially missing
DELEVE	OAK	2	25-04-2023	21-05-2023	83,7	DEMOEN	partially missing
DELIPP	OAK	2	28-04-2023	22-05-2023	112,1		LOCF
DELOEW	OAK	2	22-04-2023	10-05-2023	28,1		
DEMARB	OAK	2	17-05-2023	25-05-2023	30,7		
DEMOEN	OAK	2	10-04-2023	21-05-2023	63,5		
DEMUNC	OAK	2	03-05-2023	23-05-2023	33,1		
DKCOPE	OAK	2	10-05-2023	23-05-2023	27,5		
DKVIBO	OAK	2	12-05-2023	26-05-2023	91,8		
FRSTRA	OAK	2	23-03-2023	21-05-2023	31,9		
HUGYOE	OAK	2	22-04-2023	10-05-2023	12,4		
HUPEST	OAK	2	16-04-2023	09-05-2023	36,4		
HUSALG	OAK	2	28-04-2023	22-05-2023	76,7		
HUSZE2	OAK	2	11-04-2023	04-05-2023	55,7		
LTSIAU	OAK	2	11-05-2023	23-05-2023	39,7		
LTVILN	OAK	2	10-05-2023	16-05-2023	39,1		
MONTREAL	OAK	2	11-05-2023	22-05-2023	121,5		
NLLEID	OAK	2	03-05-2023	21-05-2023	46,1		
PLBYDG	OAK	2	23-04-2023	23-05-2023	18		
PLCRAC	OAK	2	23-04-2023	14-05-2023	49,1		
PLKATO	OAK	2	05-05-2023	18-05-2023	28,6		
PLLODZ	OAK	2	02-05-2023	18-05-2023	89,6		
PLLUBL	OAK	2	27-04-2023	23-05-2023	44,4	PLPTRY	completely missing
PLPTRY	OAK	2	27-04-2023	23-05-2023	44,4		
PLSZCZ	OAK	2	23-04-2023	23-05-2023	18	PLBYDG	completely missing
PLWROC	OAK	2	21-04-2023	18-05-2023	49,5		
QUEBEC	OAK	2	19-05-2023	29-05-2023	253,3		LOCF
SKBRAT	OAK	2	22-03-2023	11-05-2023	23,2		
SKNITR	OAK	2	22-03-2023	11-05-2023	23,2	SKBRAT	completely missing

Signature Page for VV-CLIN-003596 v1.0

Approval Task	[REDACTED]
	19-Sep-2023 14:05:01 GMT+0000
Approval Task	[REDACTED]
	19-Sep-2023 16:08:09 GMT+0000
Approval Task	[REDACTED]
	19-Sep-2023 17:49:39 GMT+0000
Approval Task	[REDACTED]
	19-Sep-2023 17:58:39 GMT+0000
Approval Task	[REDACTED]
	20-Sep-2023 06:04:11 GMT+0000

Signature Page for VV-CLIN-003596 v1.0

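### The cohort 2 birch season listed for station DELEVE (5-14 April 2023, 10 days) is very likely truncated and conflicts with how the SAP fills gaps at the same station

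*SAP*

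**What the plan says.** SAP 9.1 starts the birch pollen season (BPS) on the first of three consecutive days at or above 30 grains/m³ and stops it on the last day of the last such run. It lists three ways of handling missing counts: LOCF inside the observed season; a backup station, "For pollen stations with either very sparse data or completely missing data, each station was assigned a neighboring station as close as possible"; and LOCF over a short gap where the season was judged to have started or not yet ended.

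Appendix D gives these cohort 2 rows:

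- DELEVE birch: "DELEVE BIRCH 2 05-04-2023 14-04-2023 172,1 LOCF", with no neighbouring station.
- DELEVE alder: "DELEVE ALDER 2 07-02-2023 24-03-2023 153,8 DEMOEN partially missing".
- DELEVE oak: "DELEVE OAK 2 25-04-2023 21-05-2023 83,7 DEMOEN partially missing".
- DEMOEN birch, with no missing-data comment: "DEMOEN BIRCH 2 02-04-2023 05-05-2023 329,1".
- Another German station whose birch counts had gaps: "DEDRES BIRCH 2 17-04-2023 01-05-2023 68,2 DEMARB partially missing".

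SAP 9.2.2.3 averages the daily combined score (TCS) over the non-missing days of the listed season only. Protocol 15.15 derives the average whenever there is at least one diary entry in the season.

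**The concern.** At one station in one year, two species with gaps were referred to DEMOEN. Birch was handled by LOCF and given a season that ends before most German stations had started theirs. If that stop date reflects the missing data and not the pollen, the primary endpoint for these children is averaged over a short early part of their season. One diary entry is enough to derive the endpoint, so the score counts as observed and would not normally be imputed. The same dates feed average DSS and DMS in the BPS and, through the tree pollen season (TPS), the remaining key secondary endpoints.

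**Working it through.** The stop date cannot be re-derived because the documents contain no daily counts. What can be checked is whether the row fits the rest of Appendix D. Season length is stop − start + 1.

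**1. German birch rows, cohort 2 (2023)**

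| Station | Start | Stop | Days | Days shared with DELEVE |
|---|---|---|---|---|
| DELEVE | 5 Apr | 14 Apr | 10 | – |
| DEMOEN | 2 Apr | 5 May | 34 | 10 |
| DEBOCH | 10 Apr | 5 May | 26 | 5 |
| DELIPP | 17 Apr | 2 May | 16 | 0 |
| DELOEW | 17 Apr | 5 May | 19 | 0 |
| DEMARB | 17 Apr | 1 May | 15 | 0 |
| DEDRES (copy of DEMARB) | 17 Apr | 1 May | 15 | 0 |
| DEMUNC | 21 Apr | 5 May | 15 | 0 |

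All seven other rows stop between 1 and 5 May, and five start only after DELEVE has ended. Among all 35 cohort 2 birch rows, DELEVE is the shortest (median 22 days) and the first to stop. The next-earliest stop is 24 April, ten days later.

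**2. Days outside the listed window, against DEMOEN**

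- Before: 2-4 April = 3 days.
- After: 15 April-5 May = 16 + 5 = 21 days.
- Total: 3 + 21 = 24, and 24/34 = 71%.

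Keeping the 5 April start with the DEMOEN stop gives 31 days. Taking the full DEMOEN season gives 34.

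**3. Is DEMOEN a fair comparator?** In 2022 the DELEVE birch row carries no missing-data comment: "DELEVE BIRCH 1 22-03-2022 24-04-2022 221,4", which is 34 days. DEMOEN birch ran from 23 March to 26 April 2022, 35 days. The starts differ by 1 day, the stops by 2, and 33 days are shared. DEMOEN birch dates were also used for BEMARC in 2023, so those counts are in hand.

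**4. What the stop rule implies.** A stop on 14 April means that 12-14 April were all at or above 30 grains/m³, as observed or as filled. Had 15 April been missing and carried forward, it would also have been at or above 30 and the season would have continued. So, unless the date was set by hand after visual inspection, 15 April was either observed below threshold or missing and left unfilled. The SAP does not say which.

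**5. Oak and the tree season.** DELEVE oak names DEMOEN but starts on 25 April; DEMOEN oak starts on 10 April. Both stop on 21 May, giving 27 against 42 days. The means also differ (83.7 against 63.5), whereas the DELEVE alder row repeats DEMOEN's dates and mean exactly.

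The listed DELEVE TPS for 2023 is hazel 5-7 January (3 days), alder 7 February-24 March (46), birch 5-14 April (10) and oak 25 April-21 May (27): 3 + 46 + 10 + 27 = 86 days. The 10 days from 15 to 24 April lie in none of them. A birch stop of 5 May, or an oak start of 10 April, would each close the gap: 5 April-21 May is 47 days, and 3 + 46 + 47 = 96.

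**6. Consistency of handling.** Three of the four rows marked partially missing (DELEVE alder, DEDRES birch, DEDRES oak) carry the backup station's dates. The fourth, DELEVE oak, names the backup but not its start date. DELEVE birch has no backup.

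**The case against.** The case for leaving the row alone has several sound parts.

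- **No proof.** Without daily counts, a short local season cannot be excluded. This stands, and limits the finding to a strong inference.
- **No plain breach of the backup rule.** That rule covers very sparse or completely missing data. The birch row is marked LOCF, a permitted approach, and nothing shows that its counts were very sparse. DEMOEN is listed as backup for alder and oak only. A reader might infer that SAP 9.1 was broken; the documents support only inconsistent handling.
- **Handling by species is not unusual.** DEDRES used a backup for birch and oak but kept its own alder and hazel dates. True, but there the species with birch-season gaps were filled.
- **Short seasons occur without any flag.** DKCOPE birch lasted 4 days in 2022, MONTREAL and QUEBEC 6 days each, and HUSALG 13 days in 2023. Shortness alone therefore proves nothing. The problem is a stop date out of line with every station in the same country: HUSALG stops on 24 April, as do two other Hungarian rows, and MONTREAL and QUEBEC agree with each other to within a day.
- **The oak row may combine own and backup counts.** Possible, given its different mean, but undocumented.
- **A gap in the TPS is allowed.** SAP 9.1 says so. The gap is an issue only because both seasons bordering it are in doubt.

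Two stronger readings should also be resisted. One is that most high-exposure days are lost: Appendix D gives seasonal means, not the timing of peaks. The other is that no planned analysis could reveal the problem: SAP 9.1 describes visual inspection of the counts, and SAP 6.3.5 excludes subjects on a list of potential data issues that is not in the documents and might cover this station.

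**Conclusion.** The concern holds as a very likely truncation that needs checking and correcting, not as a proven error. If DELEVE followed DEMOEN in 2023 as closely as it did in 2022, the listed window omits about 24 of 34 birch days, 21 of them after 14 April. The TPS loses 10 days.

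Both arms at the station share the window, and the model has a random effect for pollen station within cohort. The expected consequence is noise and loss of relevant exposure; the documents do not support a claim of clear between-arm bias.

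The effect on the trial result cannot be sized because subject numbers by station are not given. As an illustration only, 500 cohort 2 subjects spread evenly over the 36 stations listed for that cohort would give 500/36 ≈ 14 children, or 1.4% of 1000. An assumed range of 0 to 40 is 0% to 4%. The overall estimate is therefore unlikely to move much, but the row defines the primary endpoint and is cheap to put right.

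**What to change.** Before unblinding:

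1. Check the DELEVE daily birch counts for 2023, above all from 15 April.
2. Where they are missing, fill them with DEMOEN counts, the backup already named for alder and oak, and re-apply the 30 grains/m³ rule to reset the stop date. Keep the 5 April start if the station's own counts support it (31 days with the DEMOEN stop); use the full DEMOEN season (34 days) only if they do not.
3. If the counts are present and below threshold, keep the row and record that as the reason.
4. Reconcile the DELEVE oak start (25 April against 10 April at DEMOEN), or document how the row was built.
5. Re-derive the BPS, oak-season and TPS averages for these subjects.

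If the listed dates are kept, or unblinding has already occurred, run a sensitivity analysis of the primary and key secondary endpoints with the DEMOEN dates.

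The cost is up to two Appendix D rows and one re-run of the endpoint derivation. No new data are needed, and Protocol 15.10 already allows inspection of the counts to lead to corrected start and stop dates.

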9.2 Derivations for the trial

9.2.1 Derivations of endpoints

9.2.1.1 Definition of DSS and DMS

During the diary completion period, symptoms and medication use are recorded daily by the subject in the e-diary. In addition, missed school days for patient, missed workdays for caregiver, and school days where performance is affected by AR/C are collected in the e-diary.

9.2.1.2 DSS

The 6 symptoms of AR/C DSS consist of 4 rhinitis symptoms (runny nose, blocked nose, sneezing, itchy nose) and 2 conjunctivitis symptoms (gritty feeling/red/itchy eyes, watery eyes). The subject rates each symptom as none, mild, moderate, or severe. Each rating is then assigned to a score from 0 to 3 based on the subject's daily rate:

0 = no symptoms

1 = mild symptoms

2 = moderate symptoms

3 = severe symptoms

The DSS is the sum of the 6 individual rhinoconjunctivitis symptom scores each day and ranges from 0 to 18.

9.2.1.3 DMS

The AR/C DMS is derived using the scoring system in Table 8 and takes values between 0 and 20 (maximum allowable daily rescue medication used). Note that the recommended dose of Desloratadine is scored 6, and that doses below are scored proportionally, i.e. if a 12-year-old takes 5 ml once daily, this is scored as 3. Similarly lower doses than recommended use of Loratadine tablets, Olopatadine eye drops, and Mometasone furoate nasal spray is also scored proportionally based on the recommended daily dose. Subjects taking Loratadine tablets, although they should have taken Desloratadine oral solution are scored the same as if they should have taken tablets, i.e. a score of 6 for 1 tablet, and a score of 3 for half a tablet. Even if a subject takes more than the allowed dosage, then it cannot score more than the max daily score for that type of rescue medication. The following rules will be applied:

- A half tablet will be scored to 0.5 x “tablet score”.

¹⁵ [name], Head of Aerobiology and Pollen, Information Research Unit, AZ Pollen Research, GmbH, [name]

- A maximum daily score of 20 will be ensured by capping individual items scores.

Table 8: Scoring for allergic rhinoconjunctivitis rescue medication usage

Rescue medication	Dosage	Score/ Dose unit	Max daily score
Loratadine, 10 mg Or Desloratadine, oral solution 0.5 mg/mL	6-12 years old and >30 kg: 1 tablet once daily as needed	6 per tablet	6
	>12 years old: 1 tablet once daily as needed		
	5 years old: 2.5 mL solution once daily as needed	6 per 2.5mL	
	6-11 years old: 5.0 mL solution once daily as needed	6 per 5 mL	
	≥12 years old: 10 mL solution once daily as needed	6 per 10 mL	
Olopatadine eye drops, 1 mg/mL	1 drop in the affected eye(s) twice daily, morning and evening as needed	1.5 pr. drop	6
Mometasone nasal spray, 50 µg/dose	5-11 years old: 1 puff in each nostril once daily as needed (max 2 puffs)	4 per puff	8
	≥12 years old: 2 puffs in each nostril once daily as needed (max 4 puffs)	2 per puff	
Maximum allergic rhinoconjunctivitis daily medication score (DMS)			20

9.2.1.4 TCS

The AR/C daily TCS is the sum of the daily DSS and DMS (that is, daily TCS=DSS+DMS) and takes values between 0 and 38.

9.2.1.6 Daily EAACI medication score

The daily EAACI medication score (DMSEAACI) is defined according to the use of symptom relieving medication as follows:

Table 9: EAACI scoring for allergic rhinoconjunctivitis rescue medication usage

Rescue medication	Dosage	EAACI component score if medication is used (0 otherwise)
Loratadine, 10 mg Or Desloratadine, oral solution 0.5 mg/mL	6-12 years old and >30 kg: 1 tablet once daily as needed	1
	>12 years old: 1 tablet once daily as needed	
	5 years old: 2.5 mL solution once daily as needed	
	6-11 years old: 5.0 mL solution once daily as needed	
	≥12 years old: 10 mL solution once daily as needed	
Olopatadine eye drops, 1 mg/mL	1 drop in the affected eye(s) twice daily, morning and evening as needed	1
Mometasone nasal spray, 50 µg/dose	5-11 years old: 1 puff in each nostril once daily as needed (max 2 puffs)	2
	≥12 years old: 2 puffs in each nostril once daily as needed (max 4 puffs)	
Maximum allergic rhinoconjunctivitis daily medication score (DMSEAACI)		2
DMSEAACI is defined as the greatest of the EAACI components for each rescue medication type i.e., DMSEAACI can takes values of 0, 1, or 2.		
Note that in DMSEAACI can take a value of 3 if a subject uses "Oral corticosteroids with/without INS, with/without H1A" (Pfaar et al. 2014). This is not relevant for this trial as oral corticosteroids are not supplied as rescue medication.		

